2.6 Study Hypothesis

We hypothesize that Cabozantinib will synergize with Pembrolizumab to improve PFS in the 2nd line setting for patients with metastatic pancreatic cancer.

3. ELIGIBILITY

3.1 Inclusion Criteria

Participants are eligible to be included in the study only if all of the following criteria apply:

- 3.1.1 Male/female participants who are at least 18 years of age on the day of signing informed consent with histologically confirmed diagnosis of pancreatic ductal adenocarcinoma, stage IV will be enrolled in this study.
- 3.1.2 Have measurable disease based on RECIST v1.1 (Response Evaluation Criteria in Solid Tumors). Lesions situated in a previously irradiated area are considered measurable if progression has been demonstrated in such lesions.
- 3.1.3 Evidence of progression or intolerance to previous standard of care pancreatic cancer systemic or locoregional therapies. Patients may have received prior radiation therapy and chemotherapy >4 weeks from start of treatment. Patients may not have been on prior clinical trial with investigational drugs for this cancer.
- 3.1.4 Have an Eastern Cooperative Oncology Group (ECOG) performance status of 0 to 1. Evaluation of ECOG is to be performed within 7-14 days prior to the first dose of study intervention. (see **Appendix A**).
- 3.1.5 Patients must have adequate organ function as defined below. Specimens must be collected within 14 days prior to the start of study intervention:
 - absolute neutrophil count $\geq 1,500/\mu\text{L}$
 - platelets $\geq 100,000/\mu\text{L}$
 - hemoglobin $\geq 9.0 \text{ g/dL or } \geq 5.6 \text{ mmol/L}$; Criteria must be met without erythropoietin dependency and without packed red blood cell (pRBC) transfusion within last 2 weeks.
 - total bilirubin $\leq 1.5 \times \text{ULN}$ or direct bilirubin $\leq \text{ULN}$ for participants with total bilirubin levels $>1.5 \times \text{ULN}$
 - AST(SGOT)/ALT(SGPT) $\leq 2.5 \times \text{ULN}$ ($\leq 5 \times \text{ULN}$ for participants with liver metastases)
 - Alkaline phosphatase $\leq 3 \times \text{ULN}$
 - International normalized ratio (INR) or prothrombin time (PT) and activated thrombo-plastin time (aPTT) $\leq 1.3 \times \text{ULN}$ unless participant is receiving anticoagulant therapy as long as PT or aPTT is within the therapeutic range of intended use of anticoagulants
 - Serum Cr or measured or calculated creatinine clearance (GFR can be used in place of Cr or CrCl) $\leq 1.5 \times \text{ULN}$ or calculated creatinine clearance $\geq 30 \text{ mL/min } (\geq 0.5 \text{ mL/sec, using Cockcroft-Gault equation})$ for participants with Cr $>1.5 \times \text{ULN}$
 - Urine protein/creatinine ratio UPCR $\leq 1 \text{ mg/mg } (\leq 113.2 \text{ mg/mmol})$
- 3.1.6 Patients must have a negative hepatitis screening test. Patients with a history of hepatitis C virus (HCV) infection must have been treated and cured. For patients with HCV infection

who are currently on treatment, they are eligible if they have an undetectable HCV viral load.

- 3.1.7 Patients with treated brain metastases are eligible if follow-up brain imaging after central nervous system (CNS)-directed therapy shows no evidence of progression.
- 3.1.8 Patients with a prior or concurrent malignancy whose natural history or treatment does not have the potential to interfere with the safety or efficacy assessment of the investigational regimen are eligible for this trial.
- 3.1.9 A male participant must agree to use a contraception during the treatment period and for 4 months after the last dose of study treatment and refrain from donating sperm during this period.

Male participants with female partners of childbearing potential are eligible to participate if they agree to one of the following during the protocol defined time frame in section X:

- Be abstinent from penile-vaginal intercourse as their usual and preferred lifestyle (abstinent on a long term and persistent basis) and agree to remain abstinent
- Use a male condom plus partner use of a contraceptive method with a failure rate of <1% per year when having penile-vaginal intercourse with a woman of childbearing potential who is not currently pregnant.
 - Note: Men with a pregnant or breastfeeding partner must agree to remain abstinent from penile-vaginal intercourse or use a male condom during each episode of penile penetration.

- 3.1.10 A female participant is eligible to participate if she is not pregnant, not breastfeeding, and at least one of the following conditions applies:

- a. Not a woman of childbearing potential (WOCBP) or
- b. A WOCBP who agrees to follow contraceptive guidance during the treatment period and for 4 months after the last dose of treatment.

A woman is considered fertile following menarche and until becoming post-menopausal unless permanently sterile (see below)

Women in the following categories are not considered WOCBP:

- Premenarchal
- Premenopausal female with 1 of the following:
 - Documented hysterectomy
 - Documented bilateral salpingectomy
 - Documented bilateral oophorectomy

Note: Documentation can come from the site personnel's review of the participant's medical records, medical examination, or medical history interview.

- Postmenopausal female
 - A postmenopausal state is defined as no menses for 12 months without an alternative medical cause.
 - A high follicle stimulating hormone (FSH) level in the postmenopausal range may be used to confirm a postmenopausal state in women not using hormonal contraception or hormonal replacement therapy (HRT). However, in the absence of

12 months of amenorrhea, confirmation with two FSH measurements in the postmenopausal range is required.

- Females on HRT and whose menopausal status is in doubt will be required to use one of the non-hormonal highly effective contraception methods if they wish to continue their HRT during the study. Otherwise, they must discontinue HRT to allow confirmation of postmenopausal status before study enrollment.

Female participants of childbearing potential are eligible to participate if they agree to use a highly effective method of contraception that has a low user dependency consistently and correctly.

Table 1. Highly Effective Contraceptive Methods That Have Low User Dependency

Highly Effective Methods That Have Low User Dependency Failure rate of <1% per year when used consistently and correctly.

 ● Progestogen- only contraceptive implant ^{a, b} ● Intrauterine hormone-releasing system (IUS) ^b ● Intrauterine device (IUD) ● Bilateral tubal occlusion

 ● Vasectomized partner A vasectomized partner is a highly effective contraception method provided that the partner is the sole male sexual partner of the WOCBP and the absence of sperm has been confirmed. If not, an additional highly effective method of contraception should be used.

 ● Sexual abstinence Sexual abstinence is considered a highly effective method only if defined as refraining from heterosexual intercourse during the entire period of risk associated with the study treatment. The reliability of sexual abstinence needs to be evaluated in relation to the duration of the study and the preferred and usual lifestyle of the participant. 
Notes: Use should be consistent with local regulations regarding the use of contraceptive methods for participants of clinical studies.
 
a) If locally required, in accordance with Clinical Trial Facilitation Group (CTFG) guidelines, acceptable contraceptive implants are limited to those which inhibit ovulation. b) If hormonal contraception efficacy is potentially decreased due to interaction with study treatment, condoms must be used in addition to the hormonal contraception during the treatment period and for at least [X days, corresponding to time needed to eliminate study treatment plus 30 days for study treatments with genotoxic potential] after the last dose of study treatment.

3.1.11 The participant (or legally acceptable representative if applicable) has the ability to understand and the willingness to provide written informed consent for the trial.

3.1.12 Able to swallow oral medication

3.2 Exclusion Criteria

Participants are excluded from the study if any of the following criteria apply:

- 3.2.1 Chemotherapy or other locoregional anti-tumoral therapies performed within 28 days of study treatment initiation.
- 3.2.2 Has received palliative radiation therapy within 2 weeks or any other radiation therapy within 4 weeks of start of study intervention. Systemic treatment with radionuclides within 6 weeks before first dose of study treatment. Participants must have recovered from all radiation-related toxicities, not require corticosteroids, and not have had radiation pneumonitis. A 1-week washout is permitted for palliative radiation (\leq 2 weeks of radiotherapy) to non-CNS disease. Subjects with clinically relevant ongoing complications from prior radiation therapy are not eligible.
- 3.2.3 Patients who have not recovered from adverse events due to prior anti-cancer therapy (*i.e.*, have residual toxicities $>$ Grade 1), unless AEs are clinically non-significant and/or stable on supportive therapy. Participants must have recovered from all AEs due to previous therapies to \leq Grade 1 or baseline. Participants with \leq Grade 2 neuropathy may be eligible.
- 3.2.4 Has received prior systemic anti-cancer therapy including investigational agents within 4 weeks prior to allocation. Participants must have recovered from all AEs due to previous therapies to \leq Grade 1 or baseline. Participants with \leq Grade 2 neuropathy may be eligible. Participants with endocrine-related AEs Grade \leq 2 requiring treatment or hormone replacement may be eligible. If the participant received major surgery, the participant must have recovered adequately from the procedure and/or complications from the procedure and/or any complications from the surgery prior to starting study intervention.
- 3.2.5 Has known active CNS metastases or carcinomatous meningitis. Participants with previously treated brain metastases may participate provided they are radiologically stable, *i.e.*, without evidence of progression for at least 4 weeks by repeat imaging (note that the repeat imaging should be performed during study screening), clinically stable and without requirement of steroid treatment for at least 14 days prior to first dose of study intervention.
- 3.2.6 Has severe hypersensitivity (\geq Grade 3) to pembrolizumab or cabozantinib and/or any of their excipients. History of allergic reactions attributed to monoclonal antibodies (mAb), compounds of similar chemical or biologic composition to Cabozantinib or Pembrolizumab.
- 3.2.7 Has received a live vaccine or live-attenuated vaccine within 30 days prior to the first dose of study drug. Administration of killed vaccines is allowed.
- 3.2.8 Has received prior therapy with an anti-PD-1, anti-PD-L1, or anti-PD-L2 agent or with an agent directed to another stimulatory or co-inhibitory T-cell receptor (*e.g.*, CTLA-4, OX-40, CD137).
- 3.2.9 Prior treatment with Cabozantinib or other receptor for MET or dual MET/HGF monoclonal antibodies or MET/HGF tyrosine kinase inhibitors.

3.2.10 Major surgery (e.g., laparoscopic nephrectomy, GI surgery, removal or biopsy of brain metastasis) within 2 weeks before first dose of study treatment. Minor surgeries within 10 days before first dose of study treatment. Subjects must have complete wound healing from major surgery or minor surgery before first dose of study treatment. Subjects with clinically relevant ongoing complications from prior surgery are not eligible.

3.2.11 Gastrointestinal (GI) disorders including those associated with a high risk of perforation or fistula formation:

- i. The subject has evidence of tumor invading the GI tract, active peptic ulcer disease, inflammatory bowel disease (e.g., Crohn's disease), diverticulitis, cholecystitis, symptomatic cholangitis or appendicitis, acute pancreatitis, acute obstruction of the pancreatic duct or common bile duct, or gastric outlet obstruction.
- ii. Abdominal fistula, GI perforation, bowel obstruction, or intra-abdominal abscess within 6 months before first dose of study treatment.
- iii. Note: Complete healing of an intra-abdominal abscess must be confirmed before first dose of study treatment.

3.2.12 Has a history of known additional malignancy that is progressing or has required active treatment within the past 3 years; or unless potentially curative treatment has been completed with no evidence of malignancy for 3 years. The time requirement does not apply to participants who underwent successful definitive resection of basal cell carcinoma of the skin, squamous cell carcinoma of the skin, superficial bladder cancer, in situ cervical cancer, or other in-situ cancers (e.g., breast carcinoma).

3.2.13 Has a diagnosis of immunodeficiency (autoimmune disease) or is receiving chronic systemic steroid therapy (in dosing exceeding 10 mg daily of prednisone equivalent) or any other form of immunosuppressive therapy within 7 days prior to first dose of study treatment.

Note: Inhaled, intranasal, intraarticular, and topical corticosteroids and mineralocorticoids are allowed. Transient short-term use of systemic corticosteroids for allergic conditions (e.g., contrast allergy) is also allowed. Replacement therapy (e.g., thyroxine, insulin, or physiologic corticosteroid replacement therapy for adrenal or pituitary insufficiency, etc.) is not considered a form of systemic treatment and is allowed.

3.2.14 Has active autoimmune disease that has required systemic treatment in the past 2 years (i.e. with use of disease modifying agents, corticosteroids or immunosuppressive drugs). Replacement therapy (e.g., thyroxine, insulin, or physiologic corticosteroid replacement therapy for adrenal or pituitary insufficiency, etc.) is not considered a form of systemic treatment and is allowed.

3.2.15 Clinically significant cardiovascular disease, for example cerebrovascular accidents (less than 6 months, CVA) /stroke, myocardial infarction (also less than 6 months), unstable angina pectoris, New York Heart Association class 3 or 4 congestive heart failure, or serious cardiac arrhythmia requiring medication.

3.2.16 Uncontrolled hypertension defined as sustained blood pressure (BP) > 140 mm Hg systolic or > 90 mm Hg diastolic despite optimal antihypertensive treatment.

3.2.17 QT interval calculated by the Fridericia formula (QTcF) > 480 ms per electrocardiogram (ECG) within 14 days before first dose of study treatment.

Note: If a single ECG shows a QTcF with an absolute value > 500 ms, two additional ECGs at intervals of approximately 3 min must be performed within 30 min after the initial ECG, and the average of these three consecutive results for QTcF will be used to determine eligibility (i.e., if the average is ≤ 500 ms the patient is eligible).

3.2.18 Concomitant anticoagulation with or plan to use oral anticoagulants (warfarin, direct thrombin and Factor Xa inhibitors) or platelet inhibitors (e.g., clopidogrel). Allowed anticoagulants are the following:

- Prophylactic use of low-dose aspirin for cardio-protection (per local applicable guidelines) and low-dose low molecular weight heparins (LMWH).
- Therapeutic doses of LMWH or anticoagulation with direct factor Xa inhibitors rivaroxaban, edoxaban, or apixaban in subjects without known brain metastases who are on a stable dose of the anticoagulant for at least 1 week before first dose of study treatment without clinically significant hemorrhagic complications from the anticoagulation regimen or the tumor.

3.2.19 Pregnant, breastfeeding, and/or lactating women. A WOCBP who has a positive urine pregnancy test within 72 hours prior to allocation will be excluded. If the urine test is positive or cannot be confirmed as negative, a serum pregnancy test will be required. Female subjects are considered to be of childbearing potential unless one of the following criteria is met: permanent sterilization (hysterectomy, bilateral salpingectomy, or bilateral oophorectomy) or documented postmenopausal status (defined as 12 months of amenorrhea in a woman over 45 years-of-age in the absence of other biological or physiological causes. In addition, females under 55 years-of-age must have a serum follicle stimulating hormone (FSH) level > 40 mIU/mL to confirm menopause).

3.2.20 Patients that are expecting to conceive or father children within the projected duration of the study, starting with the screening visit through 120 days after the last dose of trial treatment.

3.2.21 Patients with uncontrolled intercurrent illness.

3.2.22 Patients with known psychiatric illness or substance abuse disorders or other social situations that would interfere with cooperation with the requirements of the trial.

3.2.23 Inability to swallow tablets.

3.2.24 Has had an allogenic tissue/solid organ transplant.

3.2.25 Clinically significant hematuria, hematemesis, or hemoptysis of > 0.5 teaspoon (2.5 ml) of red blood, or other history of significant bleeding (e.g., pulmonary hemorrhage) within 12 weeks before first dose of study treatment.

3.2.26 Cavitating pulmonary lesion(s) related to bacterial infections or pneumonia or known endotracheal or endobronchial disease manifestation. Note that cavitating pulmonary lesion(s) related to malignancy, with the exception of central lesions measuring ≥ 4 cm, are not excluded.

3.2.27 Lesions invading or encasing major blood vessels, specifically the abdominal aorta and inferior vena cava. Encasement of local vascular structure(s) is not excluded.

3.2.28 Other clinically significant disorders that would preclude safe study participation.

- Serious non-healing wound/ulcer/bone fracture.
- Uncompensated/symptomatic hypothyroidism

3.2.29 Moderate to severe hepatic impairment (Child-Pugh B or C).

3.2.30 Is currently participating in or has participated in a study of an investigational agent or has used an investigational device within 4 weeks prior to the first dose of study intervention. Participants who have entered the follow-up phase of an investigational study may participate as long as it has been 4 weeks after the last dose of the previous investigational agent.

3.2.31 Has a history of (non-infectious) pneumonitis/interstitial lung disease that required steroids or has current pneumonitis/interstitial lung disease.

3.2.32 Has an active infection requiring systemic therapy.

3.2.33 Has a known history of Human Immunodeficiency Virus (HIV) infection. No HIV testing is required unless mandated by local health authority.

3.2.34 Has a known history of Hepatitis B (defined as Hepatitis B surface antigen [HBsAg] reactive) or known active Hepatitis C virus (defined as HCV RNA [qualitative] is detected) infection.

3.2.35 Has a known history of active TB (Bacillus Tuberculosis).

3.2.36 Has a history or current evidence of any condition, therapy, or laboratory abnormality that might confound the results of the study, interfere with the subject's participation for the full duration of the study, or is not in the best interest of the subject to participate, in the opinion of the treating investigator.

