Dose reductions or dose interruptions for hematological toxicities are not mandated but can be applied as clinically indicated. Supportive care for thrombocytopenia or anemia, such as transfusions, may be managed according to institutional guidelines. The use of colony-stimulating growth factors should be considered. Febrile neutropenia or evidence of infection associated with neutropenia must be assessed immediately and treated appropriately and in a timely manner according to institutional guidelines.

Weight Loss

Anorexia and weight loss should be managed according to local standard of care including nutritional support. Pharmacologic therapy should be considered for appetite enhancement when not prohibited by a particular protocol.

Corrected QT Prolongation

The effect of orally administered Cabozantinib 140 mg qd on QTc interval was evaluated in a placebo-controlled study in subjects with medullary thyroid cancer (MTC). A mean increase in QTcF of 10-15 ms was observed after 4 weeks after initiating Cabozantinib treatment. A concentration-QTc relationship could not be definitively established. Changes in cardiac wave form morphology or new rhythms were not observed. No Cabozantinib-treated subjects in this study had a QTcF > 500 ms. Review of the larger safety database (approximately 5000 subjects exposed to Cabozantinib in clinical trials and in post-marketing experience) confirmed the absence of safety concerns associated with QT prolongation. There were no events of torsades de pointes reported.

Concomitant treatment with strong cytochrome P450 (CYP) 3A4 inhibitors, which may increase Cabozantinib plasma concentrations, should be avoided.

If at any time on study there is an increase in QTcF to an absolute value > 500ms, two additional ECGs must be performed with intervals not less than 3-min apart within 30min after initial ECG.

If the average QTcF from the three ECGs is > 500 ms, the following actions must be taken:

- Interrupt Cabozantinib treatment
- Immediately notify the Sponsor
- Hospitalize symptomatic subjects (e.g., with palpitations, dizziness, syncope, orthostatic hypotension, a significant ventricular arrhythmia on ECG) for a thorough cardiology evaluation and management
- Consider cardiology consultation for asymptomatic subjects for evaluation and management
- Check electrolytes, especially magnesium, potassium and calcium; correct abnormalities as clinically indicated

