- Check concomitant medications for any medication that may have contributed to QT prolongation, and if possible, discontinue these medications (<http://www.qtdrugs.org>)
- Repeat ECG triplicates hourly until the average QTcF is \leq 500 msec, or otherwise determined by consultation with a cardiologist or appropriate expert.

Subjects with QTc prolongation and symptoms must be monitored closely until the QTc elevation and symptoms have resolved. Cabozantinib treatment may be restarted at a reduced dose level if all of the following conditions are met:

- Symptoms are determined to be unrelated to the QT interval prolongation
- The QTcF value > 500 ms is not confirmed
- Cabozantinib treatment has been interrupted through a minimum of 1 week following the return of the QTcF to \leq 500 ms.
- QT prolongation can be unequivocally associated with an event other than Cabozantinib administration and is treatable/has been resolved
- Sponsor has reviewed all available information and has agreed to the continuation of study treatment

Following reinitiation of study treatment, ECGs must be repeated weekly for 2 weeks, then every 2 weeks for 1 month, then according to the protocol-defined time points.

Cabozantinib treatment must be permanently discontinued if either of the following applies:

- Cardiac evaluation confirms that symptoms are the consequence of QT interval prolongation
- Recurrence of QTcF prolongation after reinitiation of study treatment at a reduced dose

Infections and Infestations

Infections are commonly observed in cancer subjects. Predisposing risk factor include a decreased immune status (e.g., after myelosuppressive anticancer therapies, splenectomy), destructive growth of the underlying malignancy including bone marrow infiltration with suppression of normal hematopoiesis, as well as the presence of IV devices.

Infections and abscesses should be treated with appropriate local care and systemic therapy. Cabozantinib should be interrupted until adequate healing has taken place.

Fatigue

Common causes of fatigue, such as anemia, deconditioning, emotional distress (depression and/or anxiety), poor nutrition, dehydration, sleep disturbance, and hypothyroidism should be ruled out and treated according to standard of care. Pharmacological management should be considered after disease specific morbidities have been excluded when not prohibited. Monitor TSH with Pembro.

Electrolyte Disorders

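### Exclusion 3.2.17 both excludes and admits a triplicate-average QTcF above 480 and up to 500 ms, and Section 7.2.3 and Table 5 disagree on what follows 20 mg daily cabozantinib

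*Combined protocol and SAP*

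**What the plan says.** **QTcF at entry.** Section 3.2 excludes a patient who meets any one of its criteria. Criterion 3.2.17 is "QT interval calculated by the Fridericia formula (QTcF) > 480 ms per electrocardiogram (ECG) within 14 days before first dose of study treatment". Its Note begins "If a single ECG shows a QTcF with an absolute value > 500 ms, two additional ECGs" and requires those two ECGs within 30 minutes of the first. The mean of the three then decides entry: "if the average is ≤ 500 ms the patient is eligible". Section 4.3.3 and the Study Calendar (Section 11) allow the screening ECG to be up to 4 weeks old. After screening, the calendar lists ECGs only when clinically indicated.

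**QTcF on study.** Section 7.2.2 has its own repeat rule: "If at any time on study there is an increase in QTcF to an absolute value > 500ms, two additional ECGs must be performed". It continues: "If the average QTcF from the three ECGs is > 500 ms, the following actions must be taken", the first action being to interrupt cabozantinib.

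**Cabozantinib reductions.** Section 7.2.3 steps down from 60 to 40 mg and from 40 to 20 mg. At 20 mg daily it allows resumption at the same dose if tolerated, and otherwise discontinuation. Table 5 in Section 8 runs from 40 mg daily (level 0) to 20 mg daily (level -1), 20 mg every other day (level -2) and discontinuation (level -3). Section 6.1 refers readers to Section 7 for dose modifications.

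**The concern.** Each pair of rules gives opposite instructions for the same patient.

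For QTcF, the physician signing the Eligibility Checklist finds an average of, say, 495 ms barred by the criterion and accepted by its Note. Letting the Note override the criterion does not cure this, because the patient with the worse first ECG then has the easier route in. The Note's 500 ms trigger and pass mark match the on-study interruption rule in 7.2.2, not the 480 ms entry limit. The screening ECG is also the only one the calendar schedules for every patient, so this is the one planned QTcF check that all patients undergo.

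For dosing, a patient who cannot tolerate 20 mg daily loses cabozantinib under 7.2.3 and keeps it at a lower dose under Table 5. What is at stake is uniform application of an eligibility rule and a dosing rule.

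**Working it through.** No sample size, power or alpha figure is involved. The check sets the rules side by side.

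**1. QTcF**

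Inputs: entry limit 480 ms (3.2.17, criterion); repeat trigger 500 ms and pass mark 500 ms on the mean of three (3.2.17, Note).

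| Screening readings (ms) | Value that decides | Criterion (> 480 excluded) | Note (mean ≤ 500 eligible) |
|---|---|---|---|
| 485 only | 485 | excluded | not triggered |
| 510, 490, 485 | (510 + 490 + 485)/3 = 495 | excluded | eligible |
| 510, 485, 475 | (510 + 485 + 475)/3 = 490 | excluded | eligible |

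In the second row all three readings exceed 480 ms, yet the Note admits the patient. The band in dispute is above 480 and up to 500 ms: 500 − 480 = 20 ms.

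Mean of the two repeats needed after a first ECG of 501 ms:
- pass mark 500 ms: (3 × 500 − 501)/2 = 499.5 ms or less;
- pass mark 480 ms: (3 × 480 − 501)/2 = 469.5 ms or less.

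ECG window: a tracing 20 days before the first dose satisfies 4.3.3 and the calendar but fails 3.2.17. A tracing within 14 days satisfies all three.

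**2. Cabozantinib ladder from the 40 mg starting dose**

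| Step | Section 7.2.3 | Table 5 |
|---|---|---|
| Start | 40 mg daily | 40 mg daily |
| First reduction | 20 mg daily | 20 mg daily |
| 20 mg daily not tolerated | stop | 20 mg every other day (20/2 = 10 mg/day on average) |
| Next | – | stop |

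The ladders differ by one step. Section 7.2.3 offers one dose below 40 mg and Table 5 offers two.

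Appendix E bears on which ladder can work. It calls for restarting at a reduced dose after recovery from Grade 3 palmar-plantar erythrodysesthesia (Table 16) and after ALT or AST above 5 and up to 8 × ULN (Table 18). For a patient already on 20 mg daily, 7.2.3 contains no lower dose, so these instructions can be followed only with level -2 of Table 5. Some patients reach 20 mg without an earlier toxicity reduction: 7.2.3 starts those with mild hepatic impairment at that dose, and 3.2.29 excludes only moderate to severe impairment. For them the disputed step is the first reduction.

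**The case against.** The strongest reply is that the documents already lean towards Table 5. Section 7.3.2 refers to Section 8 for the criteria for holding both drugs, and 7.3.3 cites Section 8 for dose modification. Section 8 is the dose-modification section and holds the levels for both drugs. Appendix E leaves permitted dose levels to the protocol, and Table 5 is the only table of levels. Section 7.2.3 starts from 60 mg, which is not this trial's dose, and reads like generic product text. This stands as a lean, and it decides the direction of the fix. It is not an explicit ranking: 7.3.2 concerns holding, 7.3.3 concerns pembrolizumab, and 6.1 still points to Section 7.

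The ECG window is also a weak conflict, since a tracing within 14 days meets every section. Aligning it is tidying.

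On QTcF, one can say that the case is narrow (a first ECG above 500 ms and a mean above 480 and up to 500 ms), that 3.2.36 lets the investigator exclude a patient anyway, and that 7.2.2 interrupts cabozantinib if an on-study mean exceeds 500 ms. All true, and all reasons to rate the point minor. None of them makes the two sentences of 3.2.17 agree.

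A reader might infer that three dosing outcomes compete: stay at 20 mg, alternate days, or stop. The text does not support that. Resuming and stopping are successive steps in one line of 7.2.3, so the conflict between the sections is two-way.

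**Conclusion.** Wrong as written in two places, minor in severity. An average QTcF above 480 and up to 500 ms is both excluded and eligible. When 20 mg daily is not tolerated, 7.2.3 and Table 5 give different next steps. Both findings rest on the current text alone and need no numerical assumption.

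Three stronger readings are tempting and should not be drawn:
- **That the Note exposes patients to a demonstrated cardiac risk.** Section 7.2.2 reports "A mean increase in QTcF of 10-15 ms was observed after 4 weeks after initiating Cabozantinib treatment", but at 140 mg, against 40 mg here. It adds "A concentration-QTc relationship could not be definitively established" and reports no torsades de pointes. The documents give no basis for projecting a rise at the trial dose.
- **That a countable number of patients is affected.** The documents give neither the frequency of such ECGs nor the number to be screened, so none can be estimated.
- **That the primary result is at risk.** Sections 9.4 and 12.1.6 analyse PFS in all patients who received study drug, so neither inconsistency changes that analysis, its power or its alpha. This conclusion relies on those two sections; 9.7.2 also mentions meeting the eligibility criteria, which is a further reason for one clear entry rule.

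**What to change.** **QTcF.** Change the end of the 3.2.17 Note so that the patient is eligible only if the average is ≤ 480 ms. Set the ECG window in 4.3.3 and the calendar to the 14 days that 3.2.17 already requires. If the sponsor in fact intends 500 ms, the criterion itself must say so.

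**Dosing.** Replace the 20 mg line in 7.2.3 with a reference to Table 5, and point 6.1 to Section 8. If level -2 is not wanted, delete it from Table 5 and state in Appendix E what a reduced dose means for a patient already on 20 mg daily.

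**Cost.** One wording amendment and a revised calendar, with no added patients or visits. The few patients whom the Note now admits with an average above 480 and up to 500 ms would be excluded. The stricter mark does bite: a first ECG of 501 ms with two repeats of 475 ms averages (501 + 475 + 475)/3 = 483.7 ms and would still exclude. Screening ECGs older than 14 days would be repeated, as 3.2.17 already demands.
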